7.2.2.3. Summaries of Laboratory Abnormalities

The following summaries (number and percentage of subjects) for treatment-emergent laboratory abnormalities will be provided by lab test and treatment group; subjects will be categorized according to the most severe postbaseline abnormality grade for a given lab test:

- Treatment-emergent laboratory abnormalities
- Treatment-emergent grade 3 or 4 laboratory abnormalities
- Treatment-emergent marked laboratory abnormalities

The summaries of treatment-emergent laboratory abnormalities will be presented by treatment group and highest grade for the placebo-controlled and active treatment period. The listing of all laboratory abnormalities will be provided.

For all summaries of laboratory abnormalities, the denominator is the number of subjects with nonmissing postbaseline values, with the baseline determined per Section 7.2.

By-subject listings of treatment-emergent Grade 3 or 4 laboratory abnormalities and marked laboratory abnormalities will be provided by subject ID number and visit in chronological order. This listing will include all test results that were collected throughout the study for the lab test of interest, with all applicable severity grades displayed.

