 - Moderately-to-severely active CLE (Cutaneous Lupus Disease Area and Severity Index [CLASI] activity score ≥ 10) at screening and Day 1
 - Prior intolerance or inadequate response to at least one of the listed medications for the treatment of CLE (Sections 4.2 and 4.3):
- Stable dose (defined as no change in prescription for at least 28 days prior to Day 1) of antimalarials and/or topical or oral corticosteroids is permitted during the study (see Section 5.6.1 for dose restrictions and other details). Subjects who are not planning to continue these medications during the study must have discontinued them at least 28 days prior to Day 1
- Must not have used prohibited medications per Section 5.6.2

Study Procedures/ Frequency:

Study visits for all subjects will occur at:

- Screening: Within 28 days prior to Day 1
- **Study Dosing Period:** Day 1 and at Weeks 2, 4, 8, 12, 14, 16, 20, and 24 or early termination (ET; if applicable)

Subjects who have not permanently discontinued study drug dosing during the first 24-week period may be eligible to enter the 24-week extension period:

- **24-week Extension Period:** Weeks 30, 36, 42, and 48 or ET (if applicable)
- Follow-Up (FU) Visit: A FU visit will be conducted 4 weeks after the last dose of study drug. Subjects who discontinue study drug ≥ 4 weeks prior to their last visit will not be asked to return for a FU visit

Screening Assessments:

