Subjects who provide written informed consent will be screened for eligibility, and undergo the following tests/procedures: complete medical history (including demographics, surgical history, and CLE history with documentation of prior skin biopsy results, if available), review of medication use, complete physical examination, height, weight, Physician's Global Assessment (PGA), CLASI, vital signs (blood pressure, heart rate, respiratory rate, and temperature), 12-lead electrocardiogram (ECG), clinical labs (chemistry, hematology, coagulation, urinalysis, and urine protein to creatinine ratio), hepatitis B virus (HBV) test, hepatitis C virus (HCV) test, human immunodeficiency virus type 1 and type 2 (HIV-1, HIV-2) test, QuantiFERON® TB Gold in Tube test (if applicable) and chest x-ray (if not obtained within 3 months prior to screening), C-reactive protein (CRP), erythrocyte sedimentation rate (ESR), hemoglobin A1c (HbA_{1c}), thyroid stimulating hormone (TSH) test, urine drug and alcohol screen, serum pregnancy test (females of child-bearing potential only, as defined per protocol), follicle stimulating hormone (FSH) test (females of non-childbearing potential only, as defined per protocol),), and adverse event (AE) collection.

Day 1 through Week 24 (Study Dosing Period) Assessments:

Eligible subjects will be randomized on Day 1. Subjects will return to the study center at Weeks 2, 4, 8, 12, 14, 16, 20, and 24 and undergo the following tests/procedures: medical history updates (Day 1 only), review of medication use, symptom-driven physical examinations, PGA, CLASI, Subject's Global Assessment and other subject-reported measures (visual analogue scales [VAS], 36-item Short Form Health Survey [SF-36], Dermatology Quality of Life Index [DLQI], and Treatment Satisfaction Questionnaire for Medication [TSQM]), weight, vital signs, 12-lead ECG (Week 24 only), clinical labs (chemistry, hematology, coagulation, urinalysis, and urine protein to creatinine ratio), HCV monitoring (Weeks 12 and 24; if applicable), CRP, ESR, fasting lipids (Day 1 and Weeks 12 and 24), urine pregnancy test (females of child-bearing potential only), quantitative serum immunoglobulin test (Day 1 and Weeks 8 and 20), autoantibody panel and complement levels (Day 1 and Weeks 12 and 24), detailed target lesion assessment, representative photographs of areas

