with skin involvement (identifying subject features should be obscured, as much as possible), detailed mucous membrane assessment (Day 1 and Weeks 2, 12, 14, and 24), and AE collection.

At Week 12, upon completion of all scheduled assessments, subjects on placebo will be re-randomized 1:1 in a blinded fashion to receive filgotinib 200 mg + PTM GS-9876 30 mg once daily or GS-9876 30 mg + PTM filgotinib 200 mg once daily for the remainder of the study.

Subjects who discontinue study drug dosing at any time may continue with study visits, procedures, and assessments, if deemed medically appropriate by the investigator, but will not be eligible for entering the 24-week extension period.

Weeks 30 through 48 (24-week Extension Period) Assessments:

Subjects who have not permanently discontinued study drug dosing in the first 24-week period may enter the subsequent 24-week extension period where they will continue to receive their assigned dose of study drug, in a blinded fashion. Subjects will return to the study center at Weeks 30, 36, 42, and 48, and undergo the following tests/procedures: review of medication use, symptom-driven physical examinations, PGA, CLASI, Subject's Global Assessment and other subject-reported measures, weight, vital signs, 12-lead ECG (Weeks 36 and 48), clinical labs (chemistry, hematology, coagulation, urinalysis, and urine protein to creatinine ratio), HCV monitoring (Weeks 36 and 48; if applicable), CRP, ESR, fasting lipids (Week 42 only), urine pregnancy test (females of child-bearing potential only), quantitative serum immunoglobulin test (Week 42 only), autoantibody panel and complement levels (Week 42 only), detailed target lesion assessment, representative photographs of areas with skin involvement (identifying subject features should be obscured, as much as possible), detailed mucous membrane assessment (Weeks 36 and 48), and AE collection.

Early Termination Visit Assessments:

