7. SAFETY ANALYSES

The safety analyses will be performed for the placebo-controlled treatment period up to Week 12, up to Week 24, and for the entire study duration. Analyses for these treatment periods will be presented by the treatment groups specified in Section 3.

For the analyses of adverse events that include data after Week 12 the exposure-adjusted analyses will be presented.

For the AEs, laboratory abnormalities and concomitant medication data, the collection/start date will be used to determine which reporting period the record belongs to. For other parameters, the nominal visits will be used.

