The CTCAE will be used to assign toxicity grades (0 to 4) to laboratory results for analysis. Grade 0 includes all values that do not meet the criteria for an abnormality of at least Grade 1. For laboratory tests with criteria for both increased and decreased levels, analyses for each direction (ie, increased, decreased) will be presented separately.

7.2.2.1. **Treatment-Emergent Laboratory Abnormalities**

Treatment-emergent laboratory abnormalities for the entire study period and in subjects discontinued treatment prematurely are defined as values that increase at least 1 toxicity grade from baseline at any postbaseline time point, up to and including the date of last dose of study drug plus 30 days for subjects who permanently discontinued study drug, or the last available date in the database snapshot for subjects who were still on treatment at the time of an interim analysis. If the relevant baseline laboratory value is missing, any abnormality of at least Grade 1 observed within the time frame specified above will be considered treatment emergent.

For the analyses of active treatment period, the baseline is the day of the first dose of active study drug administration.

For the analyses of placebo-controlled period, the lab abnormality occurring after (within 30 days) Week 12 visit is included only if subject did not continue treatment after Week 12.

The listing of all laboratory abnormalities will be provided.

7.2.2.2. **Treatment-Emergent Marked Laboratory Abnormalities**

Treatment-emergent marked laboratory abnormalities are defined as values that increase from baseline by at least 3 toxicity grades at any postbaseline time point, up to and including the date of the last dose of study drug plus 30 days for subjects who permanently discontinued study drug or the last available date in the database snapshot for subjects who were still on treatment at the time of an primary Week 12 analysis. If the relevant baseline laboratory value is missing, any Grade 3 or 4 values observed within the timeframe specified above will be considered treatment-emergent marked abnormalities.

Same rules as in the Section 7.2.2.1 apply for determination of TE abnormality in the placebo-controlled and entire study duration.

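### Active-period laboratory-abnormality percentages rest on 12 or 8 scheduled draws, so they cannot be read against the 12-week placebo column (4 draws), nor switchers against the original active arms

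*SAP*

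**What the plan says.** SAP 7.2.2.1 calls an abnormality treatment-emergent if the grade rises by at least one from baseline at any later time point, up to 30 days after the last dose. SAP 7.2.2.3 classes each subject by her most severe post-baseline grade for a test. It reports number and percentage, and the denominator is subjects with a post-baseline value, not draws or person-time. On layout it says: "The summaries of treatment-emergent laboratory abnormalities will be presented by treatment group and highest grade for the placebo-controlled and active treatment period".

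The active period has its own starting point. SAP 7.2.2.1 states: "For the analyses of active treatment period, the baseline is the day of the first dose of active study drug administration". SAP 3.8.3 and 7.2 agree. That is Day 1 for the original active arms and the start of the Week 12 drug for subjects first randomised to placebo.

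For adverse events, SAP 7 allows for unequal follow-up: "For the analyses of adverse events that include data after Week 12 the exposure-adjusted analyses will be presented". No counterpart is stated for laboratory abnormalities, or for the liver thresholds in SAP 7.2.3, which are also percentages of subjects. SAP 7.2 plans no formal testing of laboratory data.

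The Protocol Synopsis sets visits in the first 24 weeks at "Day 1 and at Weeks 2, 4, 8, 12, 14, 16, 20, and 24", and extension visits at Weeks 30, 36, 42 and 48. Protocol Appendix 2 schedules hematology, chemistry, coagulation and urinalysis at every one of them.

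**The concern.** The chance that a subject has at least one abnormal value rises with the number of times she is tested. A worst-grade percentage therefore depends partly on the visit schedule.

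For the original active arms, the draws of the placebo-controlled period are a subset of the active-period draws, from the same baseline. Their active-period percentage can hardly be lower than their 12-week percentage, whatever the drug does. Placebo treatment ends at Week 12, so no placebo column of matching length exists. Within the active-period table, switchers and original arms stand side by side with different numbers of draws.

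At stake is how the longer-term laboratory tables are read. A reader could take a higher active-period percentage for toxicity that builds up over time, or a lower switcher percentage for a milder effect, when the schedule alone would produce either pattern in expectation. The SAP already accepts this reasoning for adverse events.

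**Working it through.** The documents give no laboratory abnormality rate and no draw count, so there is no plan figure to reproduce on this point.

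**Step 1: count scheduled post-baseline draws** (Protocol Appendix 2; hematology, chemistry, coagulation and urinalysis; subject completing 48 weeks). The active period is taken to start at the first active dose, as the SAP's baseline rules imply.

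| Column | Visits (weeks) | Draws | Weeks covered |
|---|---|---|---|
| Placebo-controlled, every arm | 2, 4, 8, 12 | 4 | 12 |
| Active period, switchers | 14, 16, 20, 24, 30, 36, 42, 48 | 8 | 36 |
| Active period, original arms | all twelve visits | 12 | 48 |

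Fasting lipids are drawn at Weeks 12, 24 and 42, which gives 1, 2 and 3 draws in the same columns. The extension is optional: a subject who stops at Week 24 has 8 draws on active drug (original arm) or 4 (switcher). A follow-up draw within 30 days of the last dose can add one.

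**Step 2: percentage expected with no drug effect.** Assume the same risk p of a qualifying value at each draw. For k independent draws, P(at least one) = 1 − (1 − p)^k. At p = 2%:
- k = 4: 1 − 0.98^4 = 7.8%
- k = 8: 1 − 0.98^8 = 14.9%
- k = 12: 1 − 0.98^12 = 21.5%

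Over a range of p, and with equally correlated draws within a subject (Gaussian copula):

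| p per draw | Correlation | 4 draws | 8 draws | 12 draws |
|---|---|---|---|---|
| 1% | 0 | 3.9% | 7.7% | 11.4% |
| 2% | 0 | 7.8% | 14.9% | 21.5% |
| 5% | 0 | 18.5% | 33.7% | 46.0% |
| 2% | 0.5 | 6.4% | 10.4% | 13.4% |
| 2% | 0.8 | 4.7% | 6.5% | 7.7% |

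**Step 3: ratios.**
- Within the active-period table (12 against 8 draws, independent): 11.4/7.7 = 1.48 at 1%, and 46.0/33.7 = 1.36 at 5%. At 2% and correlation 0.8: 7.7/6.5 = 1.2.
- Across the two period tables (12 against 4 draws, 2%): 21.5/7.8 = 2.8 if independent, and 7.7/4.7 = 1.6 at correlation 0.8.

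**Step 4: scale in subjects.** Ten placebo subjects re-randomised 1:1 give about 5 switchers per drug, so one subject is 100/5 = 20 percentage points. At 2% and independence, the gap between 8 and 12 draws is worth 5 × (0.215 − 0.149) = 0.33 of a subject in a switcher column.

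**Step 5: would person-time alone repair it?** Draws per week are 4/12 = 0.33, 8/36 = 0.22 and 12/48 = 0.25. At 2% per draw, the crude rates are 7.8%/(12/52) ≈ 34, 14.9%/(36/52) ≈ 22 and 21.5%/(48/52) ≈ 23 per 100 person-years. Visits thin out after Week 24, so person-time does not equalise the columns; it only reverses the gap between the 12-week column and the others.

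**Step 6: is an equal-draw window available?** SAP Table 3 gives Weeks 14, 16, 20 and 24 as on-active Days 15, 29, 57 and 85, the same days as Weeks 2, 4, 8 and 12 for the original arms. Each column then has 4 scheduled draws (and 1 lipid draw), and at 2% with independent draws each is expected at 7.8%.

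**The case against.** These tables are descriptive. The SAP states no comparison between periods and no test, in a 50-subject proof-of-concept study. Several planned outputs do not accumulate with draws: numeric results and changes by visit, line plots by visit (SAP 7.2.1), and listings showing every result for any test with a Grade 3 or 4 abnormality (SAP 7.2.2.3). Under Protocol 7.5, abnormalities that need intervention or lead to interruption or discontinuation are recorded as adverse events, so they enter the exposure-adjusted analyses. SAP 7 also foresees a cut at Week 24. The proposed table adds only about five switchers per drug, and the artefact in such a column is a fraction of one subject.

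Much of this stands, and it limits the point to how certain columns are read. It does not remove it. The crude percentages are still the summary a reader will look at first, and nothing in the plan warns that the columns differ in follow-up. The Week 24 cut does not equalise either: original arms then have 8 draws on active drug and switchers 4.

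A reader might infer three stronger things that the documents do not support:
- **That the placebo-controlled comparison is biased.** All three arms have the same 4 scheduled draws there.
- **That later groups show more abnormalities.** Switchers start active drug later but have fewer draws than the original arms, so they are expected to show fewer.
- **That the tables carry a spread of nearly threefold.** That figure needs independent draws and takes its columns from two different period tables.

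**Conclusion.** The point holds as a limit on interpretation. With no drug effect, the expected order of percentages is 4 < 8 < 12 draws in every case calculated. Active-period laboratory percentages therefore cannot be read against the 12-week placebo column, nor switchers against original arms. The size is uncertain, because both the per-draw risk and the correlation are assumptions, and 8 and 12 draws apply to 48-week completers. At 2% per draw, the gap between switchers and original arms lies between 14.9 against 21.5% (independent) and 6.5 against 7.7% (correlation 0.8). This concerns expectation only: with about five subjects in a switcher column, the observed order can go either way. No efficacy result and no randomised safety comparison changes.

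**What to change.** In SAP 7.2.2.3, add a summary of treatment-emergent abnormalities limited to the first 12 weeks on active drug:
- Use Weeks 2, 4, 8 and 12 for the original arms and Weeks 14, 16, 20 and 24 for switchers, with the Table 3 on-active days and the active-period baseline.
- Show it beside the 12-week placebo column.

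For the longer-period laboratory tables and the liver table in SAP 7.2.3:
- Show by group the number of subjects with data, the number of draws and person-time. Include unscheduled draws, because SAP 3.8.2 counts them toward the maximum grade and Protocol 3.5.2 calls for retests, so equal scheduled draws do not guarantee equal actual draws.
- Add a footnote that these percentages are not comparable with the 12-week placebo column.

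The cost is one extra descriptive table from data already collected, with small switcher columns. Late-onset abnormalities would still appear only in the long-period table.

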7.2.3. Liver-related Laboratory Evaluations

Liver-related abnormalities after initial study drug dosing will be examined and summarized using the number and percentage of subjects who were reported to have the following laboratory test values for postbaseline measurements:

- Aspartate aminotransferase (AST): (a) > 3 times of the upper limit of reference range (ULN); (b) $> 5 \times$ ULN; (c) $> 10 \times$ ULN; (d) $> 20 \times$ ULN
- Alanine aminotransferase (ALT): (a) $> 3 \times$ ULN; (b) $> 5 \times$ ULN; (c) $> 10 \times$ ULN; (d) $> 20 \times$ ULN
- AST or ALT: (a) $> 3 \times$ ULN; (b) $> 5 \times$ ULN; (c) $> 10 \times$ ULN; (d) $> 20 \times$ ULN
- Total bilirubin: $> 2 \times$ ULN
- Alkaline phosphatase (ALP) $> 1.5 \times$ ULN
- AST or ALT $> 3 \times$ ULN and total bilirubin: (a) $> 1.5 \times$ ULN; (b) $> 2 \times$ ULN

The summary will include data from all postbaseline visits on active treatment up to 30 days after the last dose of study drug. For individual laboratory tests, subjects will be counted once based on the most severe postbaseline values. For both the composite endpoint of AST or ALT and total bilirubin, subjects will be counted once when the criteria are met at the same

postbaseline visit date. The denominator is the number of subjects in the Safety Analysis Set who have nonmissing postbaseline values of all relevant tests at the same postbaseline visit date.

The analyses will be presented for the placebo-controlled period and entire study period.

A listing of subjects who met at least 1 of the above criteria will be provided.

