3.2. Subject Grouping

In the FAS and PP Analysis Set, subjects will be grouped according to the treatment to which they were initially randomized at Study Day 1. For the analyses based on the Safety Analysis Set, subjects will be grouped according to the actual treatment that they received. The actual treatment received will be considered to differ from the randomized treatment only when subject's actual treatment differs from randomized treatment for the entire treatment period.

For the analysis of the placebo-controlled period (up to week 12), subjects will be presented by three treatment groups:

- Filgotinib 200 mg
- Lanraplenib 30 mg
- Placebo

For the analyses for the entire study duration, subjects will be grouped into five treatment groups as specified in [Table 2](#).

Table 2. Treatment Groups for the Entire Study Duration

Lanraplenib 30 mg	Lanraplenib 30 mg from Study Day 1
Filgotinib 200 mg	Filgotinib 200 mg from Study Day 1
Placebo/Lanraplenib 30 mg	Placebo up to Week 12 and lanraplenib 30 mg after Week 12
Placebo/Filgotinib 200 mg	Placebo up to Week 12 and filgotinib 200 mg after Week 12
Placebo	Placebo group with study drug withdrawn prior to or at Week 12 (did not receive drug assigned at Week 12)

For the PK analyses, subjects will be grouped according to the actual treatment they received.

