3.8. Analysis Visit Windows

3.8.1. Definition of Study Day

Study day will be calculated from the first dosing date of study drug and derived as follows:

- For post dose study days: Assessment Date – First Dosing Date + 1
- For days prior to the first dose: Assessment Date – First Dosing Date

Therefore, Study Day 1 is the day of the first dose of any study drug.

For placebo subjects who were re-randomized to active treatment at Week 12, the On-Active-Treatment study day will be calculated as: Assessment Date – Date of the first dose of active treatment + 1. The date of the first dose of the study drug dispensed at Week 12 is recorded on CRF.

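### SAP 7.2.3 limits the liver-threshold table to visits on active treatment, so, read literally, its placebo column for the placebo-controlled period has no eligible data

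*SAP*

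**What the plan says.** SAP 7.2.3 plans counts and percentages of subjects who cross set multiples of the upper limit of normal for AST, ALT, bilirubin and alkaline phosphatase, and of subjects who meet the combined transaminase and bilirubin criteria. Four sentences in the section fix its scope:

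- Opening: "Liver-related abnormalities after initial study drug dosing will be examined and summarized using the number and percentage of subjects".
- Records used: "The summary will include data from all postbaseline visits on active treatment up to 30 days after the last dose of study drug".
- Denominator: "The denominator is the number of subjects in the Safety Analysis Set who have nonmissing postbaseline values of all relevant tests", at the same visit date.
- Periods: "The analyses will be presented for the placebo-controlled period and entire study period".

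The columns come from elsewhere. SAP 7 says: "Analyses for these treatment periods will be presented by the treatment groups specified in Section 3". SAP 3.2 says: "For the analysis of the placebo-controlled period (up to week 12), subjects will be presented by three treatment groups", and lists filgotinib, lanraplenib and placebo. For the entire study, SAP Table 2 has five groups. One is a Placebo group whose members stopped by Week 12 and never took the drug assigned at Week 12.

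**The concern.** The sentence that tells a programmer which records to use names active treatment, while the sentences around it speak of study drug, the Safety Analysis Set and the placebo-controlled period. In this SAP, *study drug* includes placebo (3.1.2) and *active treatment* does not. A programmer who follows the record-selection sentence would remove all placebo data from a table whose purpose in the first 12 weeks is to set the active arms beside placebo.

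Safety and tolerability are the secondary objective. This is the only place where the SAP specifies a table of multiples of the upper limit of normal and of the transaminase-plus-bilirubin combination. If the column showed 0 of 10, a reader could not tell a zero produced by the rule from a zero that was observed. Any case in an active arm would be read against a group in which no case could have been counted.

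**Working it through.** **1. What *active treatment* means in the SAP.**

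- SAP 3.8.1: "For placebo subjects who were re-randomized to active treatment at Week 12, the On-Active-Treatment study day will be calculated as" the assessment date minus the date of the first active dose, plus 1. For these subjects the count starts with the switch.
- SAP 4.2.1: duration of active treatment for subjects randomised to placebo runs from the first day of active drug.
- SAP 7.2: there is a separate laboratory baseline for the active treatment period, taken in placebo subjects on or before the day of the first active dose.
- SAP 7.2.2.3: the placebo-controlled period and the active treatment period are named as different periods.

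None of these uses lets placebo count as active treatment.

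**2. Which placebo visits pass the filter up to Week 12.** Chemistry is scheduled at Weeks 2, 4, 8 and 12 (Protocol Appendix 2). Re-randomisation of placebo subjects follows completion of the Week 12 assessments (Protocol 3.3 and 6.4), so all four samples precede the first active dose. Eligible visits: none of 10 × 4 = 40 planned.

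SAP Table 3 does label Week 12 as day 1 on active treatment. A program that compares dates only might therefore admit the Week 12 sample of a subject who took the first active dose that day. That sample is still drawn before the dose, and SAP 7.2 allows it as the active-period baseline. Weeks 2, 4 and 8 are excluded either way.

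**3. What the column would show.** The planned placebo size reproduces from the 2:2:1 allocation: 50 × 1/5 = 10.

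| Filter applied to | Placebo numerator | Placebo denominator | Output |
|---|---|---|---|
| Numerator only (denominator sentence as written) | 0 | up to 10 | 0 of up to 10 |
| Numerator and denominator | 0 | 0 | empty |

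The wording does not settle which of the two would be produced.

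**4. Size of the distortion.** The table counts each subject once, so the unit is the subject. One placebo case left out changes that column by 1/10 = 10 percentage points. One case in an active arm is 1/20 = 5%.

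The documents give no background rate of threshold crossing. If each of 10 placebo subjects is assumed to cross a threshold with probability p, the chance of at least one true placebo case is 1 − (1 − p)^10:

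| Assumed p | Chance of at least one placebo case | Chance that the literal rule shows it |
|---|---|---|
| 2% | 18% | 0 |
| 5% | 40% | 0 |
| 10% | 65% | 0 |
| 20% | 89% | 0 |

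**5. Entire-study table.** The never-active Placebo group has no visit on active treatment, so it has no eligible data whatever its size. The documents give no rate from which to predict that size; it lies between 0 and 10. The two switched groups lose everything before the switch, which is their first 12 weeks.

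**6. Conflict with other sections.**

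- Protocol 8.6 summarises by arm all safety data from first dispensing to 30 days after the last dose.
- SAP 7.2 sets the scope of laboratory summaries as the Safety Analysis Set up to the last dose of study drug plus 30 days, with no active-only limit.
- SAP 7.2.2.1, the neighbouring rule for the placebo-controlled period, has no such limit either.
- SAP 7.7 declares no departure from the protocol's safety analyses. An active-only filter would be one.

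**The case against.** The strongest reply is that the documents already settle the intent. Protocol 8.6, the general laboratory scope in SAP 7.2, the statement in SAP 7.7, and the opening, denominator and period sentences of 7.2.3 all point to including placebo. The disputed sentence itself ends by referring to study drug. On this view the phrase is a slip that any careful programmer would query. This largely stands as an account of intent, and it is why the point is minor. It does not remove the phrase from the one sentence in 7.2.3 that defines the data.

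A second reply is that an active-only rule could be deliberate for the entire-study table, so that values recorded on placebo do not sit in columns for switched subjects. That is a reasonable analysis to want. But SAP 7.2 takes the laboratory baseline for the entire-study period before the first dose of any study drug and keeps the active-period baseline for the active treatment period. An active-only table therefore belongs under that second label.

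Three stronger readings are tempting, and the documents do not support them:

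- A reader might infer that the placebo column is bound to show 0 of 10. An empty column is equally literal, and it would be noticed at once.
- A reader might infer that placebo liver data vanish from the report. Numeric summaries (7.2.1), graded abnormalities (7.2.2.3), transaminase elevation as an event of special interest (7.1.7) and the laboratory listings (7.2) all keep placebo.
- A reader might express the entire-study loss as a share of subject-visits. Because each subject is counted once, such a share would not measure the distortion of this table.

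**Conclusion.** The concern holds as a minor internal contradiction. Followed as written, the record-selection rule in SAP 7.2.3 leaves the placebo column of the placebo-controlled table with no eligible data. The result is 0 of up to 10 or an empty column, and neither can serve as a comparator. In the entire-study table the never-active Placebo group has no eligible data, and switched subjects lose their first 12 weeks.

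This rests on two things: that *active treatment* has the same meaning in 7.2.3 as in the rest of the SAP, and that the Week 12 sample is drawn before the first active dose, as the protocol schedules it. It does not rest on any claim that the sponsor meant to leave placebo out; the context suggests the opposite. The effect is confined to one descriptive table and the listing of subjects who meet its criteria. No efficacy analysis, sample size or data collection is touched.

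**What to change.** In SAP 7.2.3, replace *on active treatment* with *on study drug (filgotinib, lanraplenib or placebo)*, and apply that wording to both the placebo-controlled and the entire-study tables. If an active-only view of re-randomised subjects is wanted, present it as a separately labelled active-treatment-period table with the active-period baseline already defined in SAP 7.2.

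The cost is one phrase. No new data are needed, and no new table unless the active-only view is added. If the SAP is already final, its Section 1 calls for the change to be documented in the clinical study report.
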